## A Pilot “Window of Opportunity” Neoadjuvant Study of Propranolol in Breast Cancer

Principal Investigator: [name]

Co-Principal Investigator: [name], MBA

### 1. **Background and Rationale:**

Despite great advances in the treatment of breast cancer over the past 2 decades, breast cancer is still a deadly disease claiming too many precious lives. According to the American Cancer Society ([www.Cancer.org](http://www.Cancer.org)) in the U.S., around 40,000 deaths occur each year secondary to breast cancer. There is a continuous need for more research and advances in this field.

Much of the research efforts over the past decade have focused on new molecular diagnostics and genomic profiling. This has promoted the development of multiple novel targeted agents, however despite these advances, several limitations persist; 1) Those agents are effective but also associated with significant toxicity and costs, and additional efforts are needed to better predict the benefit of new targeted agents; 2) Single-therapy options have been less effective than combinations of hormonal, chemotherapeutic, and new molecular drugs, demonstrating that it may be more important to hit an oncologic signaling pathway, rather than a single gene mutation; 3) In many patients molecular diagnostics do not reveal a discrete signaling pathway driving tumor growth, leading patients to depend on a general attack via chemotherapy. Therefore, identifying additional pathways and novel, more affordable treatment approaches in breast cancer remain desirable.

Sympathetic nervous system regulation of cancer cell biology and the tumor microenvironment has clarified the molecular basis for long-suspected relationships between stress and cancer progression. Several preclinical studies in a number of diverse cancer types have demonstrated that stimulation of beta adrenergic receptor (ADRB) signaling by the catecholamines epinephrine and norepinephrine regulate fundamental biological processes underlying the progression and metastasis of tumors, including promotion of inflammation, angiogenesis, migration, invasion, and resistance to programmed cell death, as well as inhibition of DNA damage repair and cellular immune response [1].

We recently reported that inhibition of catecholamine signaling using ADRB antagonists including the beta blockers propranolol, timolol, and atenolol reduces proliferation and promotes apoptosis in a large panel of sarcoma cell lines (angiosarcoma, osteosarcoma, and Ewing’s

## A Pilot “Window of Opportunity” Neoadjuvant Study of Propranolol in Breast Cancer

Principal Investigator: [name]

Co-Principal Investigator: [name], MBA

sarcoma), and inhibits sarcoma growth in a xenograft tumor model [2]. Moreover, we have demonstrated that propranolol behaves synergistically when combined with standard chemotherapy agents to enhance sarcoma cell death, suggesting that beta blockade sensitizes tumors to the cytotoxicity of these drugs [2]. Retrospective analyses in human carcinomas have shown incredible responses to beta blockade including a 57% reduction in breast cancer metastatic development [3] and a 17% reduction in patient mortality across all major cancer types [4]. Propranolol co-administered with other therapies has shown a 4.6 month increase in progression free survival and a 5.4 month increase in patient survival for pancreatic cancer (ASCO 2015, suppl 3, abstr 302); improved progression free survival in early and metastatic breast cancer (ASCO 2013, suppl; abstr e12564); a reduced risk of recurrence in melanoma patients (ASCO 2011, suppl; abstr 8524); and a sustained complete response in a patient with angiosarcoma [5].

### **2- Preliminary Observations**

[name] lab has demonstrated that ADRB proteins are strongly unregulated in breast cancers relative to normal breast tissue (**Figure 1**). Given this key finding and the published retrospective analyses showing efficacy of beta blockade in reducing metastasis and significantly improving patient survival rates [3, 4], we propose a Phase II “Window of Opportunity” trial to prospectively test the efficacy of the beta blocker propranolol in breast cancer patients at the Texas Tech Health Science Center and University Medical Center in El Paso, Texas. By ascertaining safety and potential benefits of the beta blocker propranolol in breast cancer, we would generate a novel and cost-effective strategy that would advance treatment options for cancer patients, especially those living in low resource setting.

### **3. Goals and Objectives:**

This trial is registered at [www.clinicaltrials.gov](http://www.clinicaltrials.gov) and planned as a Phase II study using the “window-of-opportunity” (WOO) design in which the treatment-free window between breast cancer diagnosis and surgical tumor resection is used to study the biological effects of the beta blocker propranolol (Figure 2). The proliferative index of the tumor after treatment will serve as the study's primary endpoint. We have strategically chosen the WOO design as it allows us to

## A Pilot “Window of Opportunity” Neoadjuvant Study of Propranolol in Breast Cancer

Principal Investigator: [name]

Co-Principal Investigator: [name], MBA

cost effectively evaluate molecular endpoints that support the efficacy of propranolol against breast cancer, and can be used to obtain subsequent larger grant funding from outside agencies for further clinical studies. WOO pre-surgical studies will expedite the process of testing propranolol in cancer patients by improving the understanding of its biologic effect early in its development, validating markers that may predict subsets of patients who will benefit from this drug, and targeting select patients in subsequent clinical trials that are powered to detect changes in clinical outcome. The following are the specific Aims of the study:

**Specific Aim #1: Evaluate the effect of the beta blocker propranolol on reducing the tumor proliferative index using Ki-67.**

**Specific Aim #2: Correlate ADRB expression and intra-tumoral catecholamine signaling to propranolol treatment efficacy.**

**Specific Aim #3: Assess the safety, toxicity and adherence to propranolol.**

**4. Research Design and Methods:** This trial will be designed as a Phase II study using the “window-of-opportunity” (WOO) design in which the treatment-free window between breast cancer diagnosis and surgical tumor resection is used to study the biological effects of the beta blocker propranolol (Figure The proliferative index of the tumor after treatment will serve as the study’s primary endpoint. We have strategically chosen the WOO design as it allows us to cost effectively evaluate molecular endpoints that support the efficacy of propranolol against breast cancer, and can be used to obtain subsequent larger grant funding from outside agencies for further clinical studies. WOO pre-surgical studies will expedite the process of testing propranolol in cancer patients by improving the understanding of its biologic effect early in its development, validating markers that may predict subsets of patients who will benefit from this drug, and targeting select patients in subsequent clinical trials that are powered to detect changes in clinical outcome.

### Pathological Assessment:

#### **Ki-67 assessment:**

To measure the proliferation rate of each tumor before and after propranolol treatment, immunohistochemical staining on the tumor sections will be performed in the UMC lab as

## A Pilot “Window of Opportunity” Neoadjuvant Study of Propranolol in Breast Cancer

Principal Investigator: [name]

Co-Principal Investigator: [name], MBA

standard of care on the pre-treatment tissue using an anti-Ki67 antibody (Abcam) based on protocols previously established in the [name] Lab. The post-treatment Ki-67 will be performed in [name] lab. This procedure is a standardized IHC method consistent with those utilized by all in-house TTUHSC pathologists. Ki-67 based proliferative index will be quantified via manual counting by an individual who is blinded to the tumor data on the same specimen and to the corresponding Ki-67 staining in the sample pair. A fixed number of 400 tumor cells in both the initial biopsies and post-treatment surgical samples will be counted from representative areas of the tumor. Comparison of positive and negative controls will be performed for quality assurance. Ki-67 is one of the most robust biomarkers that measures proliferation and according to the International Ki-67 in Breast Cancer Working Group could be important both in standard clinical practice and, particularly, within clinical trials [6]. We recently conducted a study to correlate between Ki-67, Recurrence score (RS) and Recurrence Score –Pathology – Clinical (RSPC) Assessment in Early Stage Breast Cancer and found significant concordance especially among the low and high risk groups [7]. Ki-67 staining shows relatively consistent measurements in specimens across a range of conditions used in routine fixation, tissue processing, and IHC analysis.

**Tissue Microarray (TMA)** From the original paraffin block of each tumor, so-called donor block (30 cases, post-treatment), a 3mm wide and 5mm deep punch biopsy, corresponding to the tumor site, will be cut. These punch biopsies will be re-embedded in a new paraffin block (recipient block) to create TMA (possibly all 30 cases in one block). An excel file will be created that identified all the 30 cases by only numbers. From this TMA, multiple 3-4 microns thick slides will be cut at the UMC histology lab for Immunohistochemistry and will be provided to [name]'s lab from the UMC Pathology ([name]). **The team will need at least 4 slides from post-surgery tumor.** With access to each patient sample before and after propranolol treatment, we will have the ability to perform further analysis to understand at the molecular level how beta blockade is affecting the tumors, if the tumors are responding to the treatment, and if the tumors are actively taking steps to develop resistance to the treatment. We will begin by examining the expression of ADRB receptors in each tumor. We will subsequently examine the expression of several downstream effectors of ADRB signaling (as a positive control to confirm that propranolol is indeed blocking ADRB signaling in the treated tumors) and potential mechanisms of resistance

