## A Pilot “Window of Opportunity” Neoadjuvant Study of Propranolol in Breast Cancer

Principal Investigator: [name]

Co-Principal Investigator: [name], MBA

that the tumor might be modulating to overcome propranolol inhibition.

These molecular studies, which will be performed in the [name] Lab, are important in our understanding of how propranolol is affecting the growth of breast tumors and to identify potential compensatory resistance events that may be occurring in the tumors following beta blockade.

- To carry out the above tests, all tumor sections (pre- and post-propranolol treatment) will be obtained from UMC Pathology, tissue sectioning and immunohistochemical (IHC) analysis will be performed in [name] lab using established experimental protocols.
- For all experiments, scoring for the expression of each protein will be performed in a semi-quantitatively (0, +1, +2, +3) blinded fashion for 1) the staining intensity and 2) the physical area within the tumor which the proteins stain positive.
- Immunohistochemistry scores for each tumor section will be obtained by multiplying the staining intensity with the area of antigen positivity.

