### ADRB Receptor Analysis:

The three ADRB receptors that we will be looking at are ADRB1, ADRB2 and ADRB3 (which are the three beta adrenergic receptors expressed in humans, and the target of propranolol). We will attempt to statistically correlate treatment efficacy to the expression of each ADRB receptor. Tumor samples from the initial biopsy and surgical resection will be deidentified and stained via IHC for these specific ADRB receptors in [name] laboratory. We will require 3 tumor sections per collected tumor sample to accomplish this experiment. For this analysis, we will require 15 tumor sections pre-propranolol treatment and 15 tumor sections post-propranolol treatment. Each section will need to be 5 microns in thickness, thus we will need approximately 100-150 microns of tissue from each tumor to complete the analysis.

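### As written, baseline and post-treatment Ki-67 are stained in what appear to be two laboratories, so a between-laboratory offset could not be separated from the drug effect

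*Combined protocol and SAP*

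**What the plan says.** Section 4 of the combined protocol and SAP, under Ki-67 assessment, says that "immunohistochemical staining on the tumor sections will be performed in the UMC lab as" "standard of care on the pre-treatment tissue using an anti-Ki67 antibody (Abcam"), following protocols from a named laboratory. The next sentence is "The post-treatment Ki-67 will be performed in [name] lab". The same paragraph describes the method as standardized, calls for stain controls, and has 400 cells per specimen counted by a reader who does not know the Ki-67 result of the paired sample.

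Three other places bear on who stains what:

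- **Section 4, Tissue Microarray.** Slides cut at UMC "will be provided to [name]'s lab from the UMC Pathology".
- **Section 4, the bullets after the molecular studies.** For sections from both time points, "tissue sectioning and immunohistochemical (IHC) analysis will be performed in [name] lab using established experimental protocols". The next bullet adds that "scoring for the expression of each protein will be performed in a semi-quantitatively (0, +1, +2, +3) blinded fashion".
- **Section 6, Investigational Plan.** A named laboratory takes biopsy tissue for biomarker work, while Ki-67 is described as routine work of the Pathology Department, with no time point given.

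Section 9 defines the primary endpoint as the change in proliferative index after treatment. It is tested by a two-sided paired t-test at 5%, with 25 patients needed and 30 recruited. No control group is described.

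**The concern.** If every baseline value comes from one laboratory and every post-treatment value from another, the mean paired difference estimates the drug effect plus any systematic staining difference between the laboratories. No analysis of these data can split the two, because no patient has both laboratories at one time point and there is no untreated group in which the offset would show.

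The error can run either way. If the second laboratory stains lower, the offset adds to an apparent fall in Ki-67. If it stains higher, it hides part of a real one. The trial is meant to support later grant applications, so an avoidable rival explanation for the primary result is worth removing before staining begins.

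**Working it through.** **Step 1. Are two laboratories involved?** Setting the statements side by side:

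- The Ki-67 paragraph describes the two sites differently, one for each time point.
- The microarray paragraph has slides passing from UMC Pathology to a named laboratory, which suggests separate facilities. This assumes that it is the same named laboratory as in the Ki-67 paragraph.
- The Investigational Plan separates the named laboratory's biomarker work from Ki-67 done in Pathology.
- The molecular-studies bullet points the other way if its reference to the tests above includes Ki-67. More likely it means the receptor and downstream markers: it follows directly on the molecular studies, and a 0 to +3 score does not fit an index counted on 400 cells. If it does include Ki-67, it conflicts with the Ki-67 paragraph.

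**Step 2. Reproduce the plan's power.** Inputs from section 9: mean change 10, SD 15, n = 25, two-sided alpha 0.05. I take 10 and 15 as index points and 15 as the SD of the paired change.

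- Noncentrality = (10/15) × √25 = 3.333, df = 24, critical t = 2.064.
- Power = 0.892, which agrees with the stated figure of more than 85%.
- Smallest significant mean change = 2.064 × 15/√25 = 6.2 points.

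**Step 3. Add a constant offset b.** Expected paired difference = drug effect + b, and noncentrality = (difference/15) × √25. The values of b are assumptions. The last column has b opposing a true 10-point change.

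| Offset b (points) | Noncentrality, no drug effect | False-positive rate | Power, true change 10 |
|---|---|---|---|
| 0 | 0 | 5.0% | 89.2% |
| 1 | 0.333 | 6.2% | 82.1% |
| 2 | 0.667 | 9.8% | 72.5% |
| 3 | 1.000 | 16.1% | 61.0% |

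Sensitivity: if 15 is instead the SD at each time point and the two values are uncorrelated, the SD of change is 15 × √2 = 21.2. The false-positive rates for 1, 2 and 3 points are then 5.6%, 7.4% and 10.4%. With correlation 0.5 the SD of change is again 15.

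**Step 4. Tissue margin if biopsies are re-stained.** 30 × (1 − 0.20) = 24 patients remain after the planned dropout. Power for a 10-point change with SD 15:

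| Pairs | Power |
|---|---|
| 24 | 87.8% |
| 23 | 86.3% |
| 22 | 84.6% |

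One pair can be lost to insufficient tissue, but a second takes power below 85%.

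**The case against.** The best reply is that the premise is not certain. Every laboratory name is removed, so separateness is inferred. The molecular-studies bullet may already put all immunohistochemistry for both time points in one place. If it governs Ki-67, there is no aliasing, only inconsistent wording. That stands as a reason for caution. It does not remove the point, because the documents would then contradict themselves on where the primary endpoint's baseline is stained.

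The second reply is that the plan has safeguards: a named antibody, a protocol taken from the named laboratory, controls and a blinded count. These bear on the likely size of an offset, and it may be small. But blinded counting deals with reader bias rather than stain intensity, and controls show that a run worked rather than calibrating one laboratory to another. No bridging sample, joint staining of pairs or adjustment for laboratory is described.

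The third reply is that the gain is limited, since the trial is a small single-arm pilot and biopsy and resection specimens may differ anyway. That is correct, and it limits what the fix can claim.

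A reader might infer that a between-laboratory bias is present, or that the trial's real type I error is 10% or 16%. The documents support neither. They give no evidence of an offset and no figure for one.

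**Conclusion.** The point holds as a structural weakness that is cheap to remove. On the most natural reading, laboratory and time point coincide in the primary comparison, and any constant staining offset would be counted as drug effect or would mask it.

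Its size is unknown. The range of 6.2% to 16.1% false positives for offsets of 1 to 3 points is illustrative. It rests on 25 pairs, an SD of change of 15, section 9's percentages being index points, and an offset that is the same for every patient. The conclusion that two laboratories are involved rests on inference from text with names removed.

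It would go too far to say that the primary result is invalid, or that staining in one laboratory would turn the before-after change into a clean drug effect. Differences between core biopsy and surgical specimen remain a limitation of the single-arm design whatever is done about staining.

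**What to change.** Before staining begins, reconcile the Ki-67 paragraph, the molecular-studies bullets and the Investigational Plan, and state which laboratory produces each Ki-67 value. Specify that both values used for the primary endpoint come from one laboratory chosen in advance, with the same antibody and protocol, and are read coded and in random order.

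- **Preferred, where a spare biopsy section exists:** re-stain it in the named laboratory in the same run as the surgical section, and keep the hospital result for clinical use.
- **Otherwise:** stain the surgical section at UMC by the baseline method. Biopsy and surgery are at least three weeks apart under the eligibility criteria, so if the hospital baseline slide is reused, staining batch still aligns with time point. The report should say so.

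**Cost.** About 30 slides are re-stained or moved, with no new biopsy, visit or patient. Re-staining needs one more biopsy section per patient. The ADRB Receptor Analysis paragraph states the existing demand in two ways ("We will require 3 tumor sections per collected tumor sample to accomplish this experiment" and "we will require 15 tumor sections pre-propranolol treatment and 15 tumor sections post-propranolol treatment"), so the addition is 1/3 = 33% or 1/15 = 6.7%. The documents do not show that enough tissue remains. With a margin of one lost pair after the planned dropout, availability should be checked before committing to re-staining.

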## A Pilot “Window of Opportunity” Neoadjuvant Study of Propranolol in Breast Cancer

Principal Investigator: [name]

Co-Principal Investigator: [name], MBA

that the tumor might be modulating to overcome propranolol inhibition.

These molecular studies, which will be performed in the [name] Lab, are important in our understanding of how propranolol is affecting the growth of breast tumors and to identify potential compensatory resistance events that may be occurring in the tumors following beta blockade.

- To carry out the above tests, all tumor sections (pre- and post-propranolol treatment) will be obtained from UMC Pathology, tissue sectioning and immunohistochemical (IHC) analysis will be performed in [name] lab using established experimental protocols.
- For all experiments, scoring for the expression of each protein will be performed in a semi-quantitatively (0, +1, +2, +3) blinded fashion for 1) the staining intensity and 2) the physical area within the tumor which the proteins stain positive.
- Immunohistochemistry scores for each tumor section will be obtained by multiplying the staining intensity with the area of antigen positivity.

### ADRB Receptor Analysis:

The three ADRB receptors that we will be looking at are ADRB1, ADRB2 and ADRB3 (which are the three beta adrenergic receptors expressed in humans, and the target of propranolol). We will attempt to statistically correlate treatment efficacy to the expression of each ADRB receptor. Tumor samples from the initial biopsy and surgical resection will be deidentified and stained via IHC for these specific ADRB receptors in [name] laboratory. We will require 3 tumor sections per collected tumor sample to accomplish this experiment. For this analysis, we will require 15 tumor sections pre-propranolol treatment and 15 tumor sections post-propranolol treatment. Each section will need to be 5 microns in thickness, thus we will need approximately 100-150 microns of tissue from each tumor to complete the analysis.

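### Do the conflicting tissue-section counts for the ADRB staining, and the unnamed ADRB time point, undermine the Aim 2 correlation?

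*Combined protocol and SAP*

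**What the plan says.** Section 4, ADRB Receptor Analysis, plans staining of both the biopsy and the resection for ADRB1, ADRB2 and ADRB3. On tissue it says "We will require 3 tumor sections per collected tumor sample to accomplish this experiment". The next sentence reads "For this analysis, we will require 15 tumor sections pre-propranolol treatment and 15 tumor sections post-propranolol treatment". It continues "Each section will need to be 5 microns in thickness", and concludes "thus we will need approximately 100-150 microns of tissue from each tumor to complete the analysis".

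The Tissue Microarray (TMA) paragraph of section 4 takes a 3 mm punch from each post-treatment block. From the resulting array, "multiple 3-4 microns thick slides will be cut at the UMC histology lab", and "The team will need at least 4 slides from post-surgery tumor". The paragraph then turns to molecular work on paired tissue ("With access to each patient sample before and after propranolol treatment"), starting with the ADRB receptors and going on to proteins downstream of them and to resistance mechanisms. The bulleted list that follows covers both pre- and post-treatment tissue and says that "tissue sectioning and immunohistochemical (IHC) analysis will be performed in" the research laboratory. Each protein is graded from 0 to +3 for intensity and for positive area, and the two grades are multiplied.

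Section 9 says the sample size suffices for a correlation of 80% or more between the Ki-67 change and ADRB expression, with a confidence width of 30%. Neither Specific Aim 2, nor section 4, nor section 9 says which specimen supplies the ADRB value.

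**The concern.** Taken literally, the tissue rules do not agree. Two consecutive sentences give 3 and 15 sections for what reads as the same analysis. The resection appears under two workflows, with 3-4 micron array slides cut at the hospital histology laboratory in one and 5 micron sections cut in the research laboratory in the other. The ADRB time point is also left open, so with three receptors and two specimens there are six possible correlations.

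Aim 2 is a named aim with a stated precision. The biopsy is the diagnostic core on which eligibility rests, so its tissue is limited. If a larger section requirement meant that some biopsies could not be scored, the correlation would rest on fewer patients. If biopsies were scored on sections and resections on punches, a before-after difference in ADRB would mix tissue format with treatment. If the specimen were chosen after the results were seen, the correlation could look selected.

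**Working it through.** **1. The plan's own tissue figure.** Inputs, all from ADRB Receptor Analysis: 5 microns per section; 3 sections per sample, or 15 before and 15 after treatment; 100-150 microns per tumor. Tissue = sections x thickness.

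| Reading | Per specimen | Per patient (both specimens) |
|---|---|---|
| 3 per sample | 3 x 5 = 15 microns | 6 x 5 = 30 microns |
| 15 before, 15 after | 15 x 5 = 75 microns | 30 x 5 = 150 microns |

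Working back, 100/5 = 20 and 150/5 = 30 sections. The 15 + 15 reading reproduces the upper end; the 3 + 3 reading is well below the range. No stated count gives the lower end of 100.

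**2. Could 15 be a total for the whole trial?** At 3 per sample, 30 patients need 3 x 30 = 90 sections per time point, and 15 would cover 15/3 = 5 tumors. The tissue figure is stated for each tumor, so this reading does not fit.

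**3. Can both counts be met?** Three sections match one stain per receptor. Fifteen sections contain those three and leave 15 - 3 = 12. The TMA paragraph plans further stains on the same tumors, which could use some of the rest. That use is an inference, because the 15 is stated under the ADRB heading.

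**4. Microarray or section.** No sentence says that ADRB is scored on the array; its slides are for immunohistochemistry in general. The 5 micron rule is the one given for ADRB. The section 9 correlation compares patients with one another using one ADRB value each. If all biopsies share one format and all resections share one format, each correlation is like for like across patients. Mixed formats would matter only for a before-after ADRB comparison, and the plan specifies no analysis of that kind.

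**5. The precision statement.** With correlation r = 0.80 and an assumed 95% level (section 9 gives none), the Fisher interval is tanh(atanh(0.80) ± 1.96/√(n - 3)).

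- n = 30: 1.0986 ± 1.96/√27 gives 0.618 to 0.901, width 0.283.
- n = 24, that is 30 x 0.80 after the stated 20% dropout: 1.0986 ± 1.96/√21 gives 0.586 to 0.910, width 0.324.

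At a 90% level the width at n = 24 is 0.268. The planned 30% is met at 30 patients. Whether it is met at 24 depends on the confidence level, and the section count does not enter the formula.

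**The case for a change.** The strongest case for a change is that the two counts differ five-fold (15 against 75 microns per specimen), that the larger one is stated expressly for the ADRB analysis, and that biopsy tissue is finite. On this view the laboratory should not have to guess, and settling the specimen before staining would prevent a choice guided by the data.

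Part of this stands. The text is inconsistent, and the extra sections are not explained where they are requested. The time point is missing from every place where one would look for it. If all six correlations were tested at 0.05 and were independent, the chance of at least one false positive would be 1 - 0.95^6 = 0.265. Section 9 states no such test, however. It speaks only of estimating a correlation with a given width, so that error rate cannot be charged to the plan.

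The step from section count to lost patients does not stand as a quantified problem. The documents give no biopsy tissue amount and no failure rate, so the number of patients who would go unscored is unknown. The shortfall in width at 24 patients comes from dropout and would be the same under either count.

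**Conclusion.** No change follows. The section counts are a drafting inconsistency that the tissue figure largely resolves: 15 per specimen reproduces 150 microns per patient and includes the 3 needed for the receptors. The microarray wording is ambiguous, but it does not bias the planned correlation so long as each time point uses one format for all patients. The missing time point is a gap that an analyst would fill sensibly by reporting the biopsy and resection correlations side by side, since both specimens are stained anyway. The interest in section 3 in markers that predict benefit leans toward the biopsy value.

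The effect on the primary Ki-67 comparison is nil, because it uses no ADRB data. No effect on the correlation's precision can be shown from the documents; the widths of 0.283 and 0.324 depend only on the number scored, the correlation and the confidence level. The conclusion assumes that the laboratory works to one format within each time point and that results for both specimens are reported.
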